## 3.3.2 Derivation rules

Based on their start and stop date, therapies and procedures will be allocated to each analysis phase and period during which they were administered. A therapy/procedure can therefore be reported in more than one analysis phase or period.

Analysis phases and periods are defined in section 2.2.1. Therapies/procedures with (partially) missing date(time)s will be allocated to each phase/period unless the available parts of the therapy/procedure start or stop date(time)s or prior and ongoing flags provide evidence the therapy/procedure was not taken during that period.

Based on their start and stop date(time), therapies and procedures will also be allocated into one or both of the following categories:

- Prior: any therapy/procedure that strictly started before the first IMP dose in 1905.
- Concomitant: any therapy/procedure that was taken on or after the first IMP dose in 1905.

A therapy/procedure that started before the date of first IMP dose in 1905 and continued during the study will be classified as both prior and concomitant.

Therapies/procedures with (partially) missing date(time)s will be allocated to each category unless the available parts of the therapy/procedure start or stop date(time) provide evidence not to do so.

## 3.3.3 Presentation of results

The number and percentage of participants with concomitant therapies and the number and percentage of participants with concomitant therapies by ATC class (level 1 and 3) and generic term will be tabulated using the Safety analysis set. Blank ATC levels, if any, will be shown as 'not available' in the tables. These tables will be provided overall, not by phase or period.

All prior and concomitant therapies data will be listed with detailed information about ATC classes.

All prior and concomitant procedures data will be listed.

Document template OTH.STAT.010 v3

#### **3.4 IMP** AND PREDNISONE ADMINISTRATION

# 3.4.1 Available data

For each study drug administration, the start and end date/time, the dose (in mg) and the actual volume are recorded.

For each continuous prednisone administration, the start and end date/time, and either the total daily dose (in mg) or the dose per administration (in mg) together with the frequency is recorded. This information is recorded for the prescribed dose as well as the actually administered dose. Only the actually administered dose information will be used for the analysis of exposure to prednisone.

Participants/caregivers may participate in (self-)administration training. Visits at which training took place and reasons for not following a training are recorded.

# 3.4.2 Derivation rules

The following parameters will be derived for EFG PH20 SC treatment periods and administrations:

- Number of re-treatment periods: number of treatment periods excluding treatment period 1, i.e.:
  - 0: for participants without any treatment period or only treatment period 1
  - 1: for participants with treatment period 2
  - 2: for participants with treatment period 2 and 3
  - o Etc.
- Number of administrations: sum of all administrations of study drug.
- Number of loading doses: i.e. daily doses of of 1000 mg).

The following parameters will be derived for prednisone administration:

- NCPD (in mg/kg/day)
- Cumulative prednisone dose (in mg)

Result will be rounded as detailed in section 2.3.4

SGS	Statistical Analysis Plan	
ARGX-113-1905	Final analysis	Final 1.0 of 26APR2024

The NCPD will be calculated based on prednisone equivalent doses. The prednisoneequivalent dose is calculated as [dose of ATC]\*[equivalence factor prednisone]/[equivalence factor ATC]. Following [equivalence factors] are used:

- Betamethasone [1.5]
- Cortisone [37.5]
- Deflazacort [15]
- Dexamethasone [1.5]
- Fluocortolone [10]
- Hydrocortisone [30]
- Methylprednisolone [8]
- Methylprednisolone acetate [8]
- Methylprednisolone sodium succinate [8]
- Paramethasone [4]
- Prednisolone [10]
- Prednisolone acetate [10]
- Prednisolone sodium succinate [10]
- Prednisone [10]
- Prednisone acetate [10]
- Prednylidene [12]
- Rimexolone [20]
- Triamcinolone [8]

Example: calculation of equivalent dosage of 12 mg methylprednisolone: 12\*10/8=15 mg prednisone.

Only systemic use of oral medication is included.

NCPD (mg/kg/day) is calculated for different periods (see section 3.4.3) as [the sum of (equivalent doses taking into account daily dose frequency)/(body weight in kg)]/(period duration in days) with body weight of visit closest before or at each start of prednisone equivalent medication record. If for a given day, no record exists in the CRF indicating prednisone use on that day, the dose will be assumed to be 0 mg.

Similarly, the cumulative prednisone dose (in mg) over these periods will be calculated based on the prednisone equivalent dose.

SGS	Statistical Analysis Plan	
ARGX-113-1905	Final analysis	Final 1.0 of 26APR2024

The following rules will be applied to allocate prednisone administrations to the correct period:

- Only start and stop dates (not times) will be considered
- Records with (partially) missing dates will be imputed as detailed in section 2.3.2.
- If administration date records overlap, then the doses reported in all the overlapping records will be combined.
- If an administration is reported as dose per administration with frequency, then the doses should be allocated to the correct dates, taking the start date and the frequency into account. Example:
  - o Dose: 40 mg
  - Frequency: every other day
  - o Start Stop date: 01JAN2022 03JAN2022

This will result in:

- 40 mg be allocated to 01JAN2022
- $\circ$  0 mg allocated to 02JAN2022
- 40 mg allocated to 03JAN2022
- Regardless of the time information, an administration on the day of the start of a new treatment period will only be allocated to that new treatment period, not to the period before.

The following parameters will be derived for IMP (self-)administration by participant and by caregiver:

- Number of participants/caregivers receiving the (self-)administration training.
- Number of training visits received by participant/caregiver.
- Number of participants/caregivers who were adequately trained and capable to (self-)administer EFG PH20 SC.
- Number of training visits before being considered capable to (self-)administer.

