ARGX-113-1905 provides efgartigimod PH20 SC extended treatment and retreatment options for participants who were randomized to the efgartigimod PH20 SC treatment arm in ARGX-113-1904, and provides first efgartigimod PH20 SC treatment and retreatment options for participants who were randomized to the placebo treatment arm in ARGX-113-1904.

At blinded rollover from ARGX-113-1904 into ARGX-113-1905, participants may be in different clinical stages: participants may have achieved CRmin; participants may have achieved

CR without meeting the minimal therapy criterion; participants may have achieved DC or EoC (the time at which no new lesions have developed for a minimum of 2 weeks and approximately 80% of lesions have healed) without having achieved CR; participants may have had treatment failure or a flare after having achieved CRmin.

ARGX-113-1905 evaluates the ability to (further) taper prednisone therapy and achieve CRoff (CRoff defined as the absence of new and established lesions completely healed while the participant is receiving no prednisone therapy for at least 2 months [8 weeks]), the ability to achieve CR and CRmin for participants who had not yet achieved CRmin, and the ability to treat flare; and assesses participant outcome measures and the safety, PD, PK, and immunogenicity of efgartigimod PH20 SC over the duration of the trial.

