At blinded rollover from ARGX-113-1904 into ARGX-113-1905 participants may be in different clinical stages. Participants may have achieved CRmin, participants may have achieved CR without meeting the minimal therapy criterion, participants may have achieved DC or EoC (the time at which no new lesions have developed for a minimum of 2 weeks and approximately 80% of lesions have healed) without having achieved CR, participants may have had treatment failure or a flare after having achieved CRmin.

ARGX-113-1905 evaluates the ability to (further) taper prednisone therapy and achieve CRoff, the ability to achieve CR and CRmin for participants who had not yet achieved CRmin, and the

ability to treat flare; and assesses patient outcome measures and the safety, PD, PK, and immunogenicity of efgartigimod PH20 SC over the duration of the trial. Duration of CR, time to CRoff and the effects of retreatment by the study drug will be specifically evaluated during the trial.

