#### Table 1: Phase, period and subperiod definition

Document template OTH.STAT.010 v3

CONFIDENTIAL AND PROPRIETARY

System Version: 1.0, Status: Approved, Document ID: VV-TMF-172580

SGS	Statistical Analysis Plan	
ARGX-113-1905	Final analysis	Final 1.0 of 26APR2024

Treatment period 1 is only applicable for participants who did not achieve CRmin or CRoff in 1904

Treatment	Treatment period 1 b,c	On-treatment 1	Earliest of (date of signing the informed consent form (ICF) of study 1905 and date of roll-over), with 00:00 added as time part a .	For the participants with off- treatment 1 subperiod : last IMP administration date/time in treatment period 1. For other participants: Date of week 52/EoT/ET visit, with 23:59 added as time part.
			1	For participants who don't have a week 52/EoT/ET visit: date of last contact, with 23:59 added as time part.
		Off-treatment 1	administration date/time in treatment period 1	For the participants with a next treatment period: first IMP administration date/time in next treatment period – 1 minute.
			+ 1 minute	For other participants:
			Date of week 52/EoT/ET visit, with 23:59 added as time part.	
			For participants who don't have a week 52/EoT/ET visit: date of last contact, with 23:59 added as time part.	
	Treatment n	eriod 2 is applicab	le for participants with	flare after CRmin in the roll-over

Treatment period 2 is applicable for participants with flare after CRmin in the roll-over phase or in treatment period 1 and who re-initiate IMP administration

Treatment period 2 °	On-treatment 2	First IMP administration date/time in treatment period 2	For the participants with off- treatment 2 subperiod : last IMP administration date/time in treatment period 2.
			For other participants:
			Date of week 52/EoT/ET visit, with 23:59 added as time part.
			For participants who don't have a week 52/EoT/ET visit: date of last contact, with 23:59 added as time part.

Page 18 of 84

SGS	Statistica	al Analysis Plan		
ARGX-113-1905	F	inal analysis		Final 1.0 of 26APR2024
	Off-treatment 2	Last IMP administration date/time in treatment period 2	trea adm	the participants with a next tment period: first IMP ninistration date/time in next tment period – 1 minute.
		+ 1 minute For	For	other participants:
				e of week 52/EoT/ET visit, h 23:59 added as time part.
			wee last	participants who don't have a ek 52/EoT/ET visit: date of contact, with 23:59 added as e part.
Etc c				

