Follow-up		End of treatment phase + 1 minute		e of last contact, with 23:59 ed as time part.

a In case no 1905 ICF date is available, participant data will not be considered in the analysis

b Not applicable for participants who enter 1905 on CRmin. They will start immediately in Treatment period 2 of the Treatment phase in case of flare

A new treatment period is considered for participants with a flare after achieving CRmin (ie, while being off IMP treatment). A new treatment period is not considered after temporary IMP discontinuation for an adverse event. Repeat until the last on-treatment or off-treatment subperiod.

Participants who enter 1905 on CRmin, will not have a treatment period 1 in the treatment phase, but will start immediately with treatment period 2 at first IMP intake in 1905 (ie, after the first flare in 1905). Note: treatment period 2 is defined in 1905 as the treatment period starting after the first flare within 1905. Treatment given before a first flare in 1905 is considered belonging to treatment period 1.

Adverse events (AEs) and concomitant therapies will be allocated to phases and periods as described in sections 5.1.2 and 3.3.2 respectively. All other assessments will be allocated to phases (PDAI, PD, PK, albumin and LDL-C also to periods and subperiods) based on the assessment date(time).

In case of (partially) missing date(time) fields disabling allocation, information from the visit/timepoint label and protocol schedule of activities will be used to allocate to the correct phase, period and subperiod. If this is not possible (unscheduled visits or visits on a turning point between phases, periods or subperiods), assessments will be handled as follows:

- Treatment phase vs. roll-over phase: assessments will be allocated to the treatment phase unless the available parts of the assessments start or stop date/time provide evidence for allocating to the roll-over phase.
- Treatment phase vs. follow-up phase: assessments will be allocated to the treatment phase unless the available parts of the assessments start or stop date/time provide evidence for allocating to the follow-up phase.
- On-treatment vs. off-treatment subperiod within a treatment period: assessments will be allocated to the on-treatment subperiod unless the available parts of the assessments start or stop date/time provide evidence for allocating to the off-treatment subperiod.

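### The SAP's count of re-treatment periods ignores efgartigimod exposure in 1904, so it is one too high for placebo-arm CRmin entrants and one too low for efgartigimod-arm flare entrants

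*SAP*

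**What the plan says.** SAP 3.4.2 derives the "Number of re-treatment periods: number of treatment periods excluding treatment period 1". The value is "0: for participants without any treatment period or only treatment period 1", then "1: for participants with treatment period 2", and so on upwards. SAP 3.4.3 summarises this count on the Safety analysis set.

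The period numbers come from SAP 2.2.1. Participants who enter 1905 in CRmin have no period 1, "but will start immediately with treatment period 2 at first IMP intake in 1905"; the Table 1 footnote repeats this: "They will start immediately in Treatment period 2 of the Treatment phase in case of flare". Neither sentence mentions the 1904 arm. The note under Table 1 assigns treatment given before any flare within 1905 to period 1. SAP 4.1.2.6 does not count a flare already present at the roll-over visit. The efficacy overview table in SAP 4.1.3.7 has Period 1 entries for the flare-after-CRmin status. The heading inside Table 1 says otherwise: "Treatment period 1 is only applicable for participants who did not achieve CRmin or CRoff in 1904".

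On the protocol side, section 2.1 states that the trial "provides first efgartigimod PH20 SC treatment and retreatment options for participants who were randomized to the placebo treatment arm" in 1904, and section 4.2 adds that "the effects of retreatment by the study drug will be specifically evaluated during the trial". The primary objective in section 3 lists retreatment separately from treatment and extended treatment.

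**The concern.** Whether a course is a re-treatment depends on whether efgartigimod was given before and then stopped. The SAP rule depends only on whether a flare has occurred inside 1905. The two tests disagree for a participant who reached CRmin on placebo plus prednisone in 1904 and first receives efgartigimod after a 1905 flare. They also disagree for a participant who reached CRmin on efgartigimod in 1904, stopped it, flared, and restarted at roll-over.

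At stake are the one exposure summary that names re-treatment and the interpretation of the period rows. Without a split by roll-over status, Period 2 in the placebo-arm column combines first-ever courses with second courses. Period 1 in the efgartigimod-arm column combines continued treatment with restarts. A reader could take a response on first exposure for a response to re-treatment. SAP 6.1 does not list this use of the term among its changes.

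**Working it through.** The plan gives no figure to reproduce and tests no hypothesis, so the check is to apply the rule to every type of entrant.

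**Inputs.** 1904 arm: efgartigimod (EFG) or placebo (PBO). Roll-over status (SAP 2.5): CRmin, CR, DC without CR, treatment failure, flare after CRmin. Let *k* be the number of efgartigimod courses started in 1905, and *s* the SAP period label of the first of them: *s* = 2 for CRmin entrants, otherwise 1 (SAP 2.2.1 note and the 4.1.3.7 table). Let *r* = 1 if that first course follows a CRmin stop of efgartigimod in 1904, otherwise 0. Protocol 4.2 says IMP is stopped at CRmin in 1904, so *r* = 1 for EFG-arm CRmin and flare-after-CRmin entrants who start a course in 1905. EFG-arm entrants in the other three statuses are taken as continuing one course.

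**Formulas.** SAP count = last period label - 1 = (*s* + *k* - 1) - 1. Actual re-treatments = *k* - 1 + *r*. Difference = *s* - 1 - *r*, whatever the value of *k*.

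Results for *k* = 1:

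| 1904 arm | Status at roll-over | SAP period | SAP count | Actual | Difference |
|---|---|---|---|---|---|
| EFG | CRmin | 2 | 1 | 1 | 0 |
| EFG | CR; DC without CR; treatment failure | 1 | 0 | 0 | 0 |
| EFG | Flare after CRmin | 1 | 0 | 1 | -1 |
| PBO | CRmin | 2 | 1 | 0 | +1 |
| PBO | CR; DC without CR; treatment failure | 1 | 0 | 0 | 0 |
| PBO | Flare after CRmin | 1 | 0 | 0 | 0 |

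Eight of the ten cells agree. With *k* = 2 both counts rise by one and the same two cells differ by the same amounts.

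**Column totals.** Let *a* be the PBO-arm CRmin entrants who start efgartigimod in 1905, and *b* the EFG-arm flare-after-CRmin entrants treated at roll-over. The summed count is too high by *a* in the PBO column, too low by *b* in the EFG column, and off by *a* - *b* in Total. The documents give neither number. Purely as an assumption, *a* from 0 to 20 and *b* from 0 to 10 gives a Total error from 0 - 10 = -10 to 20 - 0 = +20. With *a* = *b* = 10 the Total error is 0 while each arm column is wrong by 10.

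**Table 1 heading.** Flare-after-CRmin entrants did achieve CRmin in 1904, so the heading denies them period 1. Table 1 allows period 2 only after a flare in the roll-over phase or in period 1, which a participant dosed at roll-over for an existing flare has not had. Read literally, they have no period, while the overview table reports Period 1 results for them. Placing them in period 2 would not rescue the count: with *s* = 2 the difference is 2 - 1 - 1 = 0 in the EFG arm but 2 - 1 - 0 = +1 in the PBO arm. A rule that ignores the 1904 arm cannot be right for both.

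**The case against.** Four arguments have weight.

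- **The tables already separate most of this.** SAP 2.4.3 shows all tables by 1904 arm and Total. The CRmin and CRoff proportions, the time-to-event endpoints and the prednisone doses are repeated by roll-over status, as is IMP administration (Table 14.1.2.5.2). Reading arm and status together isolates both affected cells. This stands for those tables, though nothing in the SAP tells the reader to do it. It does not help for the by-period PDAI, PK, PD, albumin and LDL-C tables, which have no status split.
- **The primary safety endpoints do not use period numbers.** A reader might infer that the adverse event analysis of retreatment is corrupted. The documents do not support that: TEAEs are defined by dosing date plus 60 days (SAP 5.1.2), with their own subperiods in Table 2, and are tabulated over the treatment and follow-up phases combined. The count is an exposure descriptor.
- **The protocol sometimes uses the word loosely.** Section 4.3 speaks of retreatment for any flare after CRmin, without reference to arm, and the SAP states its period convention openly. This makes the placebo-arm cell partly a matter of terminology. It does not defend the other cell: on the section 4.3 wording a flare-after-CRmin entrant is being re-treated, and the SAP still gives zero.
- **IMP can include placebo (SAP definition of terms).** But SAP 3.4.2 derives the count for efgartigimod treatment periods, and the objective concerns efgartigimod.

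**Conclusion.** The point holds in a limited form. The rule miscounts two of ten arm-by-status cells, by +1 and -1 per participant, and the two errors can offset in the Total column. The placebo-arm error follows directly from the SAP text. The efgartigimod-arm error assumes that the note under Table 1 and the overview table prevail over the Table 1 heading, which is the better-supported reading. The heading is a separate contradiction that needs correcting whichever reading is adopted.

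A reader might infer that the count and the period results fail to measure retreatment at all. That goes too far: eight cells are right, and the split by arm and status lets an informed reader find the other two in most efficacy tables. What remains is the printed count, the pooled and arm-level rows, and the by-period tables without a status split.

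A reader might also try to size the placebo-arm error. Taking SAP 1.3's maximum of about 213 participants, one third to one half on placebo, 10% to 30% of those entering in CRmin, and the 45% flare figure in Protocol 2.2 gives 213 x 1/3 x 0.10 x 0.45 = 3.2 to 213 x 1/2 x 0.30 x 0.45 = 14.4. The placebo share and the CRmin entry rate are not in the documents, and the 45% is a six-month figure from another study of prednisone treatment, so this is no estimate. Nor do the documents show that either affected cell will contain anyone.

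**What to change.** Derive one flag for each 1905 course from 1904 arm and exposure together with status at roll-over:

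- **First treatment:** no earlier efgartigimod in either trial.
- **Continued treatment:** efgartigimod carried on from 1904 without a CRmin stop.
- **Re-treatment:** the course follows a CRmin stop of efgartigimod in either trial.

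Base the number of re-treatment periods in SAP 3.4.2 on this flag. If the present variable is kept, rename it as the number of treatment periods after a flare in 1905. Present the by-period PDAI, PK, PD, albumin and LDL-C tables by course type. Reword the Table 1 heading so that flare-after-CRmin entrants have a period, consistent with the note beneath it and with SAP 4.1.3.7.

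This needs no new data and no change in conduct, since SAP 2.1.2 already uses the treatment received in 1904. The cost is SAP wording, slightly more programming, and smaller cells in the tables that are split.

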## 3.4.3 Presentation of results

Number of re-treatment periods will be summarized using descriptive statistics and a frequency tabulation based on Safety analysis set.

Number of EFG PH20 SC administrations and will be summarized using descriptive statistics for following periods using Safety analysis set:

- Each treatment period separately
- Over the whole study

SGS	Statistical Analysis Plan	
ARGX-113-1905	Final analysis	Final 1.0 of 26APR2024

Cumulative prednisone dose and NCPD will be summarized using descriptive statistics for following phases/periods using Roll-over set:

- Over the roll-over phase
- Over the roll-over phase, until CRoff in the roll-over phase for participants who achieved CRoff in the roll-over phase
- Over the whole treatment phase
- Each treatment period separately
- Each treatment period separately, until CRmin within the applicable treatment period for participants who achieved CRmin within the applicable treatment period
- Each treatment period separately, until CRoff within the applicable treatment period for participants who achieved CRoff in the applicable treatment period
- Over the follow-up phase
- Over the whole study

All study drug administration data will be listed. Also, a detailed listing of prednisone administration and NCPD will be provided including prednisone equivalent doses with body weight at intake, CRmin, CRoff and end of treatment period.

Frequency tabulations with percentages will be produced for:

- Number of participants/caregivers receiving the (self-)administration training (denominator is all participants in SAF).
- Number of training visits received by participant/caregiver (denominator is number of participants/caregivers receiving training).
- Number of participants/caregivers who were adequately trained and capable to (self-)administer EFG PH20 SC (denominator is number of participants/caregivers receiving training).
- Number of training visits before being considered capable to (self-)administer EFG PH20 SC (denominator is number of participants/caregivers receiving training).
- Number of administrations by administrator and location (at home/onsite) per visit and overall.

Tables to be produced for the topline results (see list of output in section 8.1) will be presented overall and by disease status at roll-over in 1905 for all participants (PV+PF) as well as for PV participants.

